Following registration, patients should begin protocol treatment within 7 days of baseline AMT PET imaging. Issues that would cause treatment delays should be discussed with the Principal Investigator, [name] at [contact]; [contact], or contact the study coordinators. If a patient does not receive protocol therapy following registration, the patient's registration on the study may be cancelled. The study coordinator should be notified of cancellations as soon as possible.

Registration Process

To register a patient, the following documents should be completed by the research nurse or data manager and faxed or emailed to the study coordinator:

- Copies of required laboratory tests, scans.
- Signed patient consent form.
- HIPAA authorization form.
- Eligibility checklist.
- Completed registration form.

To complete the registration process, the study coordinator will:

• Register the patient on the study

Off-Study Criteria

• Patients will be considered to have gone off of study following the completion of the second AMT-PET scan. They may elect to continue telotristat ethyl therapy under the supervision of their physician as part of standard treatment. Cost of continued standard treatment will be charged to the patient's insurance and patient.

V. TREATMENT PLAN

AMT-PET Imaging

- Scan 1: Baseline within 7 days prior to the start of telotristat ethyl treatment.
- Scan 2: On day 9-14 of telotristat ethyl administration.
- Patients cannot eat protein containing foods for 6 hours prior to the AMT-PET studies, to ensure stable plasma tryptophan and large neutral amino acid levels during the duration of the study. They can have water and soft drinks.
- The final dose of telotristat ethyl on day 9-14 should be taken within 6 hours of the scan and should be taken along with high fat foods, but no protein. This may include oils, olives, low protein breads with margarine. The choice of such foods will be discussed with the patient at the time of enrollment. Note that this dietary restriction only applies for scan 2 since patients need to take telotristat ethyl with fat.
- Blood (approximately 3 tsp) will be drawn to measure drug levels and tumor hormone levels (including serotonin) in the blood prior to each scan. These will be done by the hospital and company laboratories.

Agent Administration

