Treatment will be administered on an outpatient basis. Reported adverse events and potential risks for telotristat ethyl are described in Section VI. No investigational or commercial agents or therapies other than telotristat ethyl may be administered with the intent to treat the patient's malignancy other than somatostatin analog (long-acting release [LAR], depot.

Agent	Dose	Route	Schedule
Telotristat ethyl	250 mg	Oral	Three times daily for 9-14 days prior to the second scan, with one dose or two doses depending on the time of Scan 2.*

*Patients may elect to stay on telotristat ethyl (250 mg tid) indefinitely following the completion Scan 2 if it is considered to provide benefit by their treating physician as part of the standard of care. As part of the study the patient will received 28 days of drug and may continue to use it and then obtain standard treatment on the agent if desired by the patient and their physician.

Benefits:

Telotristat ethyl (250 mg tid) daily compared to placebo has been shown to improve cancer related diarrhea (Kulke et al., 2017) and may slow tumor growth (Morse et al., 2020).

VI. ADVERSE EVENTS: LIST AND REPORTING REQUIREMENTS

This study will use the descriptions and grading scales found in the revised NCI Common Terminology Criteria for Adverse Events (CTCAE) version 4.0 will be utilized for AE reporting. All appropriate treatment areas should have access to a copy of the CTCAE version 4.0. A copy of the CTCAE can be

downloaded from the CTEP web site (http://ctep.cancer.gov/protocolDevelopment/electronic_applications/ctc.htm#ctc_40).

Reporting Adverse Events

In the unlikely event that any immediate toxicity is found during the course of treatment, it will be recorded and reported as described below. Given the dose of drug, no measurable delayed toxicity is expected.

		Reporting Obligation for A, B, and
	Reaction	C
А.	All life-threatening events (Grade 4), which may be due to drug	Within 24 hours (note 1)
В.	All fatal events (Grade 5) while on study (or within 24 hour	Written report to follow within 10
	of treatment).	working days (note 1).
C.	First occurrence of any previously unknown clinical event (regardless of grade).	(Note 2 and 3)

- Note 1: Telephone number available 24 hours daily: [name] page [contact] [name], [contact] (Recorder after hours). Also may report to [contact] and [contact]
- Note 2: A list of all known toxicities can be found in the protocol document or consent form.

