- peripheral edema (leg swelling) 7%
- flatulence 7%
- decreased appetite 7%
- fever 7%

In another placebo-controlled clinical trial of patients with carcinoid syndrome diarrhea and less than 4 bowel movements per day, the following additional adverse reactions, not listed above, of abdominal pain (including upper and lower abdominal pain, abdominal distention and gastrointestinal pain) and constipation were reported in at least 5% of patients in the telotristat ethyl treated group and at an incidence greater than placebo. Discontinue telotristat ethyl if severe constipation or severe persistent or worsening abdominal pain develops

Less Common Adverse Reactions:

The following is a list of adverse reactions occurring in less than 5% of patients receiving telotristat ethyl during the 12-week placebo-controlled period of the clinical trial:

Investigations: increased alkaline phosphatase, increased alanine aminotransferase, and increased aspartate aminotransferase.

Fecaloma was reported in one patient treated with telotristat ethyl during the 36-week open-label extension period following the 12-week double-blind period of the trial.

'Attribution' of the AE will be defined by the investigative team

- Definite The AE *is clearly related* to the study treatment
- Probable The AE *is likely related* to the study treatment
- Possible The AE *may be related* to the study treatment
- Unlikely The AE *is doubtfully related* to the study treatment
- Unrelated The AE *is clearly NOT related* to the study treatment

VII. MEASUREMENT OF EFFECT: AMT PET SCAN ACQUISTION AND ANALYSIS

Baseline AMT-PET scan will be obtained within 7 days of the start of telotristat ethyl 250 mg po tid and then again 9-14 days after the start of treatment under protocol 2011-053 as described below.

PET imaging will be performed using a GE Discovery STE PET/CT system (GE Medical Systems, Milwaukee, WI), located at the PET Center, Children's Hospital of Michigan. Patients will be imaged in a supine (on their back) position on a PET/CT scanner in a high-sensitivity mode.

Patients cannot eat protein containing foods for 6 hours prior to the AMT-PET studies, to ensure stable plasma tryptophan and large neutral amino acid levels during the duration of the study. The final dose of telotristat ethyl should be taken within 6 hours of the scan and should be taken along with high fat foods, but no protein (as described in the Treatment Plan).

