A venous line will be established for injection of AMT tracer (0.1 mci/kg). All PET images will be corrected for attenuation using the CT scan. After injection a CT scan is performed, immediately followed by a 60-minute dynamic PET scan of the area of interest that includes the tumor. The total dose for the PET/CT scan will be in compliance with guidelines for research studies prescribed by the Code of Federal Regulation.

Quantitative assessment of AMT tumor uptake. The AMT uptake in ROIs representing tumor and non-tumor tissue will be characterized in the following two ways:

1. Standardized uptake values (SUVs): The SUV calculation relates tracer concentration in tissue to the dose injected and the subject's mass (SUV = tissue concentration in ROI /injected dose per weight). First, decay-corrected time-activity curves will be generated to evaluate the tumoral accumulation and washout of the tracer during the scanning period. Since all subjects receive the same injected dose based upon weight (0.1 mCi/kg), the SUV images will be directly obtained by averaging values from frames of the dynamic image sequence during which time there is the most metabolic product. The timing of these frames will be determined after examination of the time-activity curves to identify the optimal time frame when tracer uptake reaches a plateau. The Standard Uptake Value maximum (SUVmax) will measure the most active pixel in the tumor and the two adjacent planes. Change in SUVmax will serve as the primary aim. Regions of Interest (ROIs) for the SUVmean will be drawn using isocontours set at 50% of the SUVmax. Results will be indicated as percent change in the uptake between the two scans.

2. Compartmental modeling (in tumors with the left ventricle of the heart in the field-of-view). In addition to the semi-quantitative SUV analysis, in tumors where the left ventricle of the heart is in the field-of-view, we will also assess the data with tracer kinetic analysis using a 3-compartment model, as described in our previous studies in lung and breast tumors (Juhasz et al., 2009; 2012). This analysis will allow a more detailed analysis of tumoral tracer transport and trapping parameters at baseline and their changes after TPH inhibitor treatment.

3. Primary endpoint and secondary endpoints:

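### High-fat, protein-free food is required before Scan 2 but this protocol sets no matching food for Scan 1, so any effect of that food on AMT uptake could not be separated from the drug effect

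*Combined protocol and SAP*

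**What the plan says.** Section V (Treatment plan, AMT-PET Imaging) sets two food rules.

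- **Both scans.** No protein for 6 hours beforehand, "to ensure stable plasma tryptophan and large neutral amino acid levels during the duration of the study". On drinks it adds: "They can have water and soft drinks".
- **Scan 2 only.** The last dose is taken within 6 hours of the scan with fatty, protein-free food; the examples are oils, olives and low-protein bread with margarine. On the items: "The choice of such foods will be discussed with the patient at the time of enrollment". On scope: "Note that this dietary restriction only applies for scan 2 since patients need to take telotristat ethyl with fat".

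The dosing table in the same section lets the number of doses on the scan day vary, "with one dose or two doses depending on the time of Scan 2". Section VII repeats the food rule, "The final dose of telotristat ethyl should be taken within 6 hours of the scan and should be taken along with high fat foods", and gives no Scan 1 counterpart. Neither section asks for food or its timing to be recorded. The blood drawn before each scan is for drug and tumor hormone levels; tryptophan and other amino acids are not named.

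Sections VII and VIII make the primary endpoint the proportion of patients whose SUVmax falls by 20% or more between the scans, in a single-arm study of 6 evaluable patients. No adjustment for diet is planned.

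**The concern.** In a before-and-after comparison without a control group, whatever changes systematically between the two scans is attributed to treatment. Here two things change by design: the drug is added, and a fatty, protein-free meal becomes obligatory. The example foods include bread, so carbohydrate may differ as well as fat. Before Scan 1 this document neither requires nor bars such food.

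If the meal lowered AMT uptake, some patients could cross the 20% threshold without any drug effect. If it raised uptake, true responders could be missed. The paired t test on the SUVs would move in the same way. The confidence interval covers sampling error only, and enrolling more patients would not remove the problem. The protocol itself treats food before the scan as relevant to this tracer, since it restricts protein for that reason.

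**Working it through.** **1. The plan's own figure.** Section VIII gives a one-sided 90% Clopper-Pearson lower limit of 0.201 for n = 6 at an expected proportion of 0.5, that is 3 of 6. The limit is the 0.10 quantile of Beta(3, 4) = 0.2009, which agrees. The planned two-sided exact 95% interval at 3/6 is 0.118 to 0.882. This point disputes neither figure, and the fix leaves both unchanged.

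**2. The two scans side by side, as this document specifies them.**

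| | Scan 1 | Scan 2 |
|---|---|---|
| Protein, previous 6 hours | not allowed | not allowed |
| Water, soft drinks | allowed | allowed |
| High-fat, protein-free food | no rule | required with last dose, within 6 hours |
| Record of food and time | none asked for | none asked for |
| Telotristat ethyl | no | yes |

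The required food and the drug enter together in every patient. The primary analysis has no contrast that separates them.

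**3. Illustration of size.** The documents give no SD for the change in SUVmax and no food effect, so both are assumed. Let the percent change be Normal with mean (drug + food) and SD 10, 15 or 20 points. A responder has a change of −20 or lower:

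P(responder) = Φ((−20 − drug − food)/SD); expected responders = 6 × P.

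Example: drug −20, food +5, SD 10 gives Φ(−0.5) = 0.309, and 6 × 0.309 = 1.85.

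| Mean drug change | Food shift, all six | Expected responders of 6 (SD 10 / 15 / 20) |
|---|---|---|
| 0 | 0 | 0.14 / 0.55 / 0.95 |
| 0 | −2 | 0.22 / 0.69 / 1.10 |
| 0 | −5 | 0.40 / 0.95 / 1.36 |
| 0 | −10 | 0.95 / 1.51 / 1.85 |
| −20 | 0 | 3.00 / 3.00 / 3.00 |
| −20 | +2 | 2.52 / 2.68 / 2.76 |
| −20 | +5 | 1.85 / 2.22 / 2.41 |
| −20 | +10 | 0.95 / 1.51 / 1.85 |
| −30 | 0 | 5.05 / 4.49 / 4.15 |
| −30 | +5 | 4.15 / 3.78 / 3.59 |
| −40 | 0 | 5.86 / 5.45 / 5.05 |
| −40 | +10 | 5.05 / 4.49 / 4.15 |

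A mean fall of 20% gives the planned 50% responders in this model and is the most sensitive case.

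If only three of six patients are affected, expected responders = 3 × P(no shift) + 3 × P(shift). With no drug effect and −5 this gives 0.27 / 0.75 / 1.16. With a 20% fall and +5 it gives 2.43 / 2.61 / 2.70.

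**4. Paired t test.** Applied for illustration to the percent change (two-sided 5% level assumed, 5 df, noncentrality food × √6/SD), with no drug effect. The chance of a significant fall for SD 10 / 15 / 20 is 2.5% at food 0; 6.0 / 4.6 / 3.9% at −2; 16.9 / 9.9 / 7.3% at −5; and 50.7 / 26.5 / 16.9% at −10.

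**The case against.** The strongest reply is that nothing in the documents says fat or carbohydrate alters AMT uptake. The one dietary route they name is plasma tryptophan and large neutral amino acids, and protein is restricted identically before both scans. This stands. A reader might infer that the meal does bias the endpoint; the documents do not support that, nor any direction or size.

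Second, a reader might call intake before Scan 1 uncontrolled. That also goes too far. Both scans run under imaging protocol 2011-053, which is not supplied and may set its own preparation rules. The most that can be said is that this document specifies nothing. The line on drinks could also be taken to mean a fast from solid food before Scan 1, but the contrast would then be fasted against fed, which does not remove the difference.

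Third, partial checks exist. Section VII says: "The AMT uptake in ROIs representing tumor and non-tumor tissue will be characterized in the following two ways". It might be inferred that background is compared with tumor at baseline only. Objective 2a points that way, but in Section VII the reference to baseline is attached to visibility, and the clause on percent difference carries no such limit. The text is ambiguous. If non-tumor regions are measured at both scans, they could reveal a general shift in uptake, though they do not adjust the primary endpoint. Kinetic modeling applies only "in tumors where the left ventricle of the heart is in the field-of-view, we will also assess the data with tracer kinetic analysis", and it does not adjust SUVmax either.

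Fourth, the size rests wholly on assumed inputs. A 10-point food shift is half the response threshold, and a uniform shift in all six patients is a strong assumption when food and timing vary. A 5-point shift in three patients moves the expected count by only about 0.1 to 0.2 with no drug effect and 0.3 to 0.6 at a 20% fall. This stands, and it keeps the priority low.

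Last, the protocol gives a reason: the drug must be taken with fat. That explains the food at Scan 2. It is no reason against the same food before Scan 1.

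**Conclusion.** The point holds as an avoidable risk of confounding, of unknown size and direction. The food difference is stated in the protocol, coincides exactly with the drug, and cannot be separated from it by the planned primary analysis.

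Under the assumed Normal model with SD 10 to 20 points, the risk matters most when the drug effect is absent or near 20%, and is small when it is large. With a 40% fall, even a +10 shift in all six leaves the chance of 3 or more responders at 92% to 99%. Three of 6 is only the sample-size benchmark here, since Section VIII states no decision rule. The reductions of up to 35% and of 40–80% cited in Section II are for tracer trapping in rat brain under other inhibitors, so they do not settle which case applies. If the food has no effect, nothing changes. A shift of about one responder is small beside an interval of 0.12 to 0.88, but that interval does not account for it.

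This is a cheap improvement of low priority and does not block the trial.

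**What to change.** Replace the Scan 2-only note in Section V, and match it in Section VII, with:

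> On the day of each scan the patient eats the same high-fat, protein-free food, in the same amounts and at the same intervals before tracer injection, including any food taken with an earlier same-day dose at Scan 2 that falls within 6 hours of the scan; telotristat ethyl is added only at Scan 2.

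Record food and time at both scans, and confirm that imaging protocol 2011-053 permits it. Food may still differ between patients; it needs to match only within a patient. The clause on an earlier dose is needed because the dosing table allows one or two doses on the day of Scan 2. Stating in Section VII that non-tumor regions are measured at both scans would make the partial check explicit.

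The cost is one changed instruction in two sections, one patient instruction and one line on the case report form. No extra patients, scans, visits or assays are needed. The downsides are a small burden before Scan 1 and a baseline, including the one used for objective 2a, that is less comparable with AMT scans done without such food.

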Bosnyak et al., 2015; 2016; 2017). High AMT transport and trapping was detected in cerebral gliomas, meningiomas as well as lung cancers and breast cancers, with various tumor types showing differences in tryptophan uptake and kinetics. Importantly, increased AMT uptake was commonly detected even in low-grade gliomas and meningiomas (Juhasz et al., 2006; 2011; Alkonyi et al., 2012; Bosnyak et al., 2015). Increased uptake and trapping of AMT in various tumors may have been affected by increased transporter activity as well as increased activity of enzymes converting tryptophan to its metabolites.

Tryptophan PET imaging in carcinoid tumors. Most NETs have an overactive serotonin pathway with increased TPH activity, thus inducing carcinoid syndrome, a condition associated with tumoral secretion of serotonin and clinical symptoms of diarrhea, flushing, bronchial constriction, as well as the development of cardiac valvular fibrosis. Diarrhea is one of the most prominent symptoms of carcinoid syndrome. Imaging TPH activity *in vivo* by PET would be useful to visualize these tumors and evaluate baseline TPH enzyme activity as well as monitor efficacy of TPH inhibitor drugs. Although AMT-PET has not been tested in carcinoid tumors, studies with other amino acid PET radiotracers, including a tryptophan derivative (¹¹C-5-hydroxy-tryptophan) demonstrated high sensitivity to detect carcinoid tumors as small as 5mm in diameter (Koopmans et al., 2008). Highest sensitivities (81-92%) were achieved in lesions located in bone, abdomen/pelvis, liver, head and neck regions. These data make it likely that AMT-PET will be able to detect carcinoid tumors in various locations, and it is reasonable to assume that its uptake and kinetic properties will be modulated by changes in tumoral TPH activity.

Serotonin and cancer proliferation. Many studies have demonstrated that serotonin may a play an important role in tumor growth and vascularity of breast, prostate, and many other tumor types (Siddiqui et al., 2006; Sonier et al., 2006; Dizeyi et al., 2011; Sarrouilhe et al., 2015). At high levels serotonin may promote tumor proliferation, while at lower levels it may even inhibit growth, in part from decreasing tumor blood supply. This is evident in studies using a number of serotonin receptor agonists and antagonists, which have stimulated or inhibited growth depending on the concentration.

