Telotristat ethyl is an oral small-molecule TPH inhibitor that has a high molecular weight and acidic moieties, which inhibit it from crossing the blood-brain barrier (Liu et al., 2008; Lapuerta et al., 2015). As the drug has recently become available for clinical treatment of carcinoid-related diarrhea, there is an urgent need to evaluate non-invasive techniques to assess drug effects.

Telotristat ethyl has been shown to inhibit tumor growth in a retrospective study of 200 patients with NET (Morse et al., 2020). After initiation of telotristat ethyl they observed a mean decrease of 0.6 cm in tumor size (p = 0.006) and decrease in tumor growth (p = 0.045). It will be of interest to determine using AMT-PET if we can measure inhibition of serotonin synthesis and serve as a biomarker in studies assess this activity of this pathway. The use of telotristat ethyl may inhibit tumor proliferation and the image of AMT uptake may provide a predictive marker of this effect. If promising, PET imaging with AMT or an ¹⁸F-labeled analog (with a longer half-life) (see, e.g., Michelhaugh et al., 2016; Giglio et al., 2017) could be useful to monitor effectiveness of TPH inhibition in future multicenter studies and clinical trials.

The central hypothesis of this pilot study is that (i) that telotristat ethyl (Xermelo[™]) (Kulke et al., 2017), a recently FDA-approved TPH inhibitor drug, will decrease tumoral AMT uptake and trapping as compared to values measured at baseline before the start of treatment. (ii) carcinoid tumors will show increased AMT uptake on PET, as compared to surrounding non-tumor tissue at baseline.

As a first step, in this pilot study we will perform AMT-PET imaging in 6 evaluable patients with previously diagnosed mNETs, not previously treated with TPH inhibitor, to characterize the baseline and post-treatment uptake patterns of these tumors and test the feasibility to use AMT-PET for evaluating activity of TPH after inhibitor treatment.

III. PATIENT SELECTION

Inclusion:

- 1. Eligible patients must be \geq 18 years of age.
- 2. Histopathologically confirmed, well-differentiated metastatic NETs
- 3. Receiving stable-dose somatostatin analog (long-acting release [LAR], depot) for > 3 months before enrollment.
- 4. Patients with 5-HIAA levels above or below the upper limit of normal range and those with unknown values at baseline are allowed to participate.
- 5. Able to lie within the PET scanner for at least 70 minutes while undergoing scanning.

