- 6. ECOG performance status of 2 or better.
- Physical exam, CBC and Multiphasic (including electrolytes, BUN, creatinine, total bilirubin, AST, and ALT) must be done within 28 days of PET imaging and demonstrate adequate renal and liver function. Creatinine ≤ 2.5, total bilirubin ≤ 1.5 x upper limit of normal (ULN). AST and ALT ≤ 2.5 ULN.
- 8. Patient must have a least one lesion greater than 2 cm on standard imaging (CT, MR, octreotide, or dotatate imaging within 8 weeks of the start of the study) that is judged amenable to AMT-PET.
- 9. Women of child bearing potential must not be pregnant or breastfeeding. A negative urine or blood pregnancy test must be obtained in women with child bearing potential. Men and women with reproductive potential must agree to use adequate contraception (hormonal or barrier method of birth control; abstinence) on study entry and for the duration of study participation.
- 10. Eligible and consent signed for imaging with AMT PET under protocol 2011-053.

Exclusion:

- Because of the risk of acute complications from severe diarrhea, patients experiencing more than 12 watery bowel movements per day associated with volume contraction, dehydration, or hypotension, or showing evidence of enteric infection are excluded.
- 2. Patients are excluded if they had undergone tumor-directed therapy within 3 months.
- 3. Patients cannot be on a targeted agent (e.g., sunitinib or everolimus) or receiving cytotoxic chemotherapy (e.g., capecitabine or temozolimide). They can't be on telotristat ethyl. Previous use is acceptable if the patient has been off for over one month.

IV. REGISTRATION PROCEDURES

General Guidelines

Eligible patients will be entered on the study centrally at the clinical trials office of the Karmanos Cancer Center/Wayne State University by the study coordinator.

At the time of registration:

- Patients must have signed an informed consent form.
- Confirm that all required prestudy history and physical examination, and laboratory tests have been collected.
- Document demographic information including smoking history. Also document medications.
- Patients should be scheduled for pre-treatment AMT-PET scans if patients have provided appropriate consent.
- Inform patients about all necessary follow-up including laboratory tests and further PET imaging.

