The proportion of patients who achieved SUVmax reduction of 20% or more between baseline and followup will be the primary measurement. We will also assess if the NET is visible above background at baseline and will also quantify the percent difference in AMT uptake between the tumor mass and background. In addition, using time-activity curves, we will also identify the optimal time frame where tumoral AMT uptake peaks. The change in SUVmean will also be measured.

VIII. STATISTICAL PLAN

Design This is a single arm single institution prospective proof-of-concept study. **Primary endpoint** is the proportion of patients who achieved SUVs reduction of 20% or more. The primary endpoint will be reported as proportions with two-sided exact 95% confidence limit. The other categorical endpoints will be reported as mean and standard deviation. Paired t test will be used for pre- and post- treatment SUVs if normality assumption holds. The relationship of one PET parameter to another will be visualized with scatter plot and measured using linear regression models. Statistical analysis will be performed using R version 3.3.2. **Power calculation:** This is a Proof-of-Concept trial where the goal is to demonstrate the feasibility and to show the proportion of patients who achieved SUVs reduction is at least 0.2 or higher. Hence, we will calculate the minimum sample size to achieve a confidence lower limit no less than 0.2. A sample size of 6 produces a one-sided 90% lower-limit confidence interval at (0.201, 1) using Clopper-Pearson formula when the expected proportion is 0.5. **Study Duration**: The accrual rate is 6/year and minimum follow -up for each patient will be 3 months. The study will require 15-18 months to complete.

IX. DATA AND SAFETY MONITORING/STUDY AUDITS/STUDY ETHICS

Data and Safety Monitoring

- 1. Scheduled meetings will be held monthly or more frequently depending on the activity of the protocol. These meetings will include the protocol investigators and research staff involved with the conduct of the protocol.
- 2. During these meetings the investigators will discuss:
 - Safety of protocol participants (adverse events and reporting)
 - Validity and integrity of the data (data completeness on case report forms and complete source documentation)

- Enrollment rate relative to expectation of target accrual, (eligible and ineligible participants)
- Retention of participants, adherence to the protocol and protocol deviations
- Protocol amendments

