- 3. Data and Safety Monitoring Reports (DSMR) of the research meetings will be completed by the Study Coordinator and submitted to the Data and Safety Monitoring Committee quarterly for review.
- 4. The Barbara Ann Karmanos Cancer Institute, Data and Safety Monitoring Committee (DSMC) provide the primary oversight of data and safety monitoring for KCI Investigator-initiated trials.

Data Management

Study data including patient images and blood sample results will be maintained by the [name]' laboratory. In addition, a KCI CTO monitor specialist will remotely review the clinical trial data. Frequency of monitoring will be based on accrual but will occur at least once every 2 months if a patient has been enrolled. Monthly screening and enrollment logs will be sent to the KCI lead Study Coordinator.

Study Audits

Authorized representatives of FDA, a regulatory authority or Wayne State University Institutional Review Board (IRB) may visit the center to perform audits or inspections, including source data verification. The investigator should contact Clinical Trials Office immediately if contacted by a regulatory agency about an inspection at his center regarding this study.

Ethics

The study will be performed in accordance with ethical principles that have their origin in the Declaration of Helsinki and are consistent with ICH/Good Clinical Practice, applicable regulatory requirements.

The final study protocol, including the final version of the Written Informed Consent Form, must be approved in writing by Wayne State University IRB.

The principal investigator is responsible for informing the Wayne State University IRB of any amendments to the protocol. The protocol must be re-approved by the IRB annually. Progress reports and notifications of serious, unexpected adverse drug reactions will be provided to the IRB. The Principal Investigator is also responsible for providing the IRB with reports of any serious adverse drug reactions from any other study conducted with the investigational product.

The principal investigator will ensure that the subject is given full and adequate oral and written information about the nature, purpose, possible risk and benefit of the study. Subjects must also be notified that they are free to discontinue from the study at any time. The subject should be given the opportunity to ask questions and allowed time to consider the information provided. In accordance with

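### Does the plan need a pre-specified analysis of the drug and serotonin levels drawn before each scan?

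*Combined protocol and SAP*

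**What the plan says.** Section V (Treatment Plan, AMT-PET Imaging) provides for sampling at both scans: "Blood (approximately 3 tsp) will be drawn to measure drug levels and tumor hormone levels (including serotonin) in the blood prior to each scan". Section IX (Data Management) covers what happens to the results: "Study data including patient images and blood sample results will be maintained by the" investigators' laboratory. Those are the only places where the blood results appear.

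The objectives in Section I are all PET measures. The primary is change in tumor SUVmax. The three secondary objectives are baseline tumor against non-tumor uptake, compartmental modeling, and SUVmean. The endpoints in the Protocol Summary and Section VII follow the same list. Section VIII plans an exact interval for the proportion with an SUV reduction of at least 20%, a paired t test on SUVs, and one analysis of association: "The relationship of one PET parameter to another will be visualized with scatter plot and measured using linear regression models".

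The Background (Section II) sets a broader purpose. The pilot is to "test the feasibility to use AMT-PET for evaluating activity of TPH after inhibitor treatment", and the authors add: "It will be of interest to determine using AMT-PET if we can measure inhibition of serotonin synthesis". They also note that tracer uptake in various tumors "may have been affected by increased transporter activity as well as increased activity of enzymes converting tryptophan to its metabolites".

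**The concern.** The study wants to know whether a PET signal reflects enzyme inhibition, and it measures two things that bear on that: whether drug was present, and whether serotonin moved. It then plans no use for either. There is no control arm, so each patient's before-and-after change has to be read alone.

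Several features let exposure and baseline biology vary:

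- Scan 2 may fall anywhere from day 9 to day 14, with one or two doses that day and the last dose at any point in the preceding 6 hours.
- 5-HIAA may be high, normal or unknown at entry.
- Current users of the drug are excluded, but for former users "Previous use is acceptable if the patient has been off for over one month".

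A patient whose SUVmax does not fall by 20% might have had little drug on board, no serotonin response, or a lesion in which the tracer is insensitive. The planned analyses do not separate these. Kinetic modeling distinguishes transport from trapping, but it is available only "in tumors where the left ventricle of the heart is in the field-of-view". What would be at stake is the interpretation of individual responders and non-responders.

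**Working it through.** **1. What the primary result depends on.** Inputs from Section VIII: n = 6, expected proportion 0.5 (3 of 6), one-sided 90% Clopper-Pearson limit.

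- Lower limit = Beta quantile(0.10; x, n − x + 1) = Beta quantile(0.10; 3, 4) = 0.2009. The plan states 0.201, so its figure is reproduced.
- Check: P(X ≥ 3 | n = 6, p = 0.2009) = 0.100.
- The two-sided exact 95% interval that will be reported for 3 of 6 is 0.118 to 0.882.

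The inputs are the number of patients and the number with a 20% SUV reduction. No blood value enters, and Section VIII attaches no decision rule that a blood value could alter.

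**2. How much information is unassigned.** Counting drug level and serotonin only: 6 patients × 2 scans × 2 measures = 24 values.

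- Six are scan 1 drug levels. Patients cannot be on the drug at entry, so these serve as a negative control and should be near zero.
- Six are scan 2 drug levels.
- Twelve are serotonin values, which form six before-and-after changes.

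The interpretable content is therefore about two numbers per patient, 12 in all. That fits in a six-row table.

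**3. What a formal analysis could show at n = 6.** The documents give no correlation between SUVmax change and either blood measure, so the true values below are an assumed range.

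- Critical Pearson correlation, two-sided 5%, 4 degrees of freedom: r = t/√(4 + t²) with t = 2.776, so r = 2.776/√11.71 = 0.811.
- Rank correlation, all 720 orderings: p = 0.033 at |rho| = 0.886 and p = 0.058 at 0.829. Only a near-perfect ordering reaches 5%.
- Fisher interval, atanh(r) ± 1.96/√3: an observed r of 0.5 gives −0.52 to 0.93, and 0.8 gives −0.03 to 0.98.

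| Assumed true correlation | Power at n = 6 |
|---|---|
| 0.5 | 17% |
| 0.7 | 37% |
| 0.8 | 56% |
| 0.9 | 82% |

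Anything added could only be descriptive: a listing and an untested plot. If serotonin fell by a similar amount in all six patients, the plot would show little pattern even if the tracer worked.

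**4. Whether blood levels answer the transporter question.** The Background remark on transporters explains raised uptake across other tumor types, namely gliomas, meningiomas, lung and breast cancers. It is not about change within a patient under a TPH inhibitor. The same section cites rat data in which a TPH inhibitor cut trapping by 40–80%, while blocking protein synthesis had no significant effect. Neither a blood drug level nor blood serotonin separates transport from trapping in the imaged lesion, so the suggested addition would leave that question where it is.

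**The case for a change.** The best case for a change is that it costs almost nothing. The samples are already drawn, patients give blood for these assays, and a few sentences in Section VIII would say how the results will be used. Several hormones are measured at two time points, so naming the display in advance would guard against showing only the comparison that looks favorable. With an interval as wide as 0.118 to 0.882, patient-level reading carries much of the pilot's value, and a listing needs no statistical power.

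Part of this stands. The omission is confirmed by reading every section, a scan 2 drug level would document exposure, and a table of SUVmax change beside drug level and serotonin change would help a reader. It does not follow that the plan is defective. The documents are silent on reporting these values. They do not say the values will go unreported, and Section IX retains them. An untested listing with no rule for reading it would be much the same whether named now or drawn up at the end. With six patients every row can be shown, so there is little room for selection. Blood serotonin is also an indirect marker of enzyme activity in one lesion, and the table would not validate the tracer.

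**Conclusion.** No change is needed. The plan pre-specifies no use of the drug and serotonin results, but this is missing detail and contradicts nothing in the stated objectives, which are confined to PET. The effect on the primary proportion, its interval, the paired SUV comparison and the sample size is nil. The possible gain is interpretive: about two extra numbers for each of six patients, which the investigators can set beside the SUVmax changes in the report, described as exploratory.

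This rests on two assumptions: that the assays are done and the results kept as Sections V and IX describe, and that the study is read as the small proof-of-concept pilot it claims to be. A later study meant to qualify AMT-PET as a marker of TPH inhibition would need a stated pharmacodynamic analysis.
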